# M. Study Design and Methods:

- Is this a clinical trial?
  - 1.1. If yes, what type? Check all that apply. N/A (no medications used)
    Phase I
    Phase II
    Phase III
    Phase IV
  - 1.2. If yes, this study must be registered on Clinicaltrials.gov.

HRPP Approval: 06/15/2011 R&D Approval: 07/05/2011 File: K: New IRB Forms

1.

Page 6 of 42

#### 2. Design

2.1. What research methods will be used in the project? Check all that apply.

| Surveys/Questionnaires  | Interviews    | Audio Taping                          |
|-------------------------|---------------|---------------------------------------|
| Behavioral Observations | Chart Reviews | Video Taping                          |
| Focus Groups            | Randomization | Double-Blind                          |
| Control Group           | Placebo       | Withhold/Delay Treatment              |
| Specimen Collection     | Deception     | Telephone Survey                      |
| Other (Describe)        |               | · · · · · · · · · · · · · · · · · · · |

2.2. Describe how randomization or other treatment assignment will be made. The RCT will involve random assignment of 250 consenting subjects at the Cpl.

Michael J. Crescenz VAMC, and 100 at the VA TVHS . For practical reasons,

neither subjects nor the intervention providers will be blinded to subject assignment. Subject assignment will be a 50/50 ratio to V-WHI care or BHL usual care (no V-WHI care). Participants are not required to engage in BHL clinical care. Both groups are permitted to use other services through their own VA or other insurance coverage or out-of-pocket expenditures. With attrition at our site, we expect 225 at initial follow-up (month 4 to 5) and 200 at final follow-up (month 9); attrition rates of 10% and, in total, 20%.

The randomization procedure will be automated within full/part-time group using a block randomization technique within group, where part-time is defined as less than 30 hours per week. Each block of 4 will contain 2 V-WHI and 2 BHL, randomly ordered. The small block sizes assure an even flow of new cases to the counselors.

- 2.3. For retrospective research studies, provide the "look-back" period. (e.g., December 1, 1999 through December 31, 2008.) N/A
- 3. **Study Duration** 
  - Provide the estimated length of time to enroll all subjects and complete the study. 44 3.1. months will complete subject data collection; 48 months will complete analysis, reporting, and dissemination.
  - 3.2. Explain the expected duration of subject participation including any follow-up. Each V-WHI subject requires 4 months of intervention. A booster session for V-WHI subjects will be provided at 8 months post-baseline. At the end of the first intervention period, which is month 4 to 5, all subjects will be invited to complete the first follow-up survey (T1). At month 9 (T2), all subjects will be invited to complete a final follow-up survey.
  - 3.3. Specify the projected date of completion of the proposed study. 11/30/2017

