Eligible veterans will be randomized at the baseline visit. The veteran will be informed of his/her group assignment and instructed how to proceed. For those patients assigned to the V-WHI intervention, the study therapist will have access to both the clinical and study baseline assessment data. The assigned counselor may view the data and begin the process of scheduling the first telephone session.

The assigned V-WHI therapists will attempt to begin treatment within 7 days after assignment. The V-WHI treatment period will last for 4 months. At month 8, the V-WHI will provide a booster session. V-WHI care is entirely telephonic.

Recruitment of VA TVHS participants is outlined in the TVHS VA protocol approved by the VA TVHS. Study staff at the VA TVHS will recruit participants from clinics at the VA TVHS and its CBOCs; enrollment and baseline visits for VA TVHS participants will take place at the VA TVHS or its CBOCs. VA TVHS participants will be consented using the consent and HIPAA approved by VA TVHS 's IRB. All V-WHI therapy and follow-ups will be conducted by staff at the VA TVHS who are also approved and listed on the VA TVHS study staff form. Study therapists will be provided access to VA TVHS clinical records. VA TVHS staff will not have access to any of the CMCVAMC participants' information/data; all databases will be separate for the two sites.

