### The BHL Program – Usual Care

Usual care will consist of standard behavioral health care at each respective VAMC. Usual care at the Cpl. Michael J. Crescenz VAMC will consist of standard behavioral health care as offered by standard operating procedures within the BHL program. The BHL program triages Primary Care patients and engages patients with appropriate behavioral health services based on patient symptoms and patient preference. Patients are triaged to care with a BHL provider or to specialty Mental Health (MH) care. Those referred to specialty MH are enrolled in the BHL's Referral Management program, an intervention designed to enhance engagement into MH care. Treatment with a BHL provider is brief and focused and may include pharmacotherapy support using psychoeducation; symptom, adherence, and side effect monitoring; and problem focused advice or action plans. Typically, care delivered within the BHL consists of of one or two 30minute sessions per month for up to 6 months. These brief and focused sessions can either be by telephone or in-person. The therapy provided as part of BHL is built upon problem-solving therapy principles, motivational interviewing principles, and the development of action plans. Finally, the BHL clinical staff are continuously assessing patients for the need for a higher level of care and facilitating the transition to more specialized services as needed. It does not duplicate any of the V-WHI components and is assumed to be complementary to them. Patients who choose to refuse clinical behavioral health care are not excluded from participating in the study.

HRPP Approval: 06/15/2011 R&D Approval: 07/05/2011 File: K: New IRB Forms Page 10 of 42

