# R. Subject Recruitment (characteristics of the study population)

- Provide the planned or targeted enrollment at:
- 1.1. CMCVAMC - 250 randomized
- 1.2. Other sites - VA TVHS VAMC - 100 randomized
- 1.3. Not applicable; chart review or use of previously collected data -

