**Power Analysis and Sample Size** 

In this study, we wish to power the study to obtain an effect size that represents a minimally clinically important difference on the health outcomes and an economically important difference related to work productivity impact (the primary endpoint). Currently, MCID is established for the PHQ-9(2) and the PCS and MCS for the VR-12.

For the PHQ-9, we anticipate that the average subject will have an average baseline score of 15 on a 0-27 scale. A clinically-meaningful reduction of 5 points, which is stated in the literature, would have 100% power to be detected. For PCS and MCS, a clinically-meaningful 5-point improvement would afford 99% power.

With regard to Hypothesis 2, corresponding to the study's power to detect an economically important difference, the primary criterion is whether an ROI greater than 1 can be obtained. This analysis is described in the following section.

For presenteeism, a reduction of 1.2% in productivity loss (or a relative improvement of 1.2%) would have comparable value to the maximum expected cost of treatment, meaning that the economic value of treatment would exceed the cost. A sample size of 100 treatment and 100 controls after subject dropout would achieve an 83% power for this outcome. To be sure of getting these numbers based on previous success rates, we will recruit 250 subjects prior to 50-50 randomization within full time and part time strata.

4.2. Define plans for data and statistical analysis, including key elements of the statistical plan, stopping rules and endpoints.

In this section, we describe the methods for testing hypothesis 1, several additional analyses including testing related to the secondary study outcomes and sensitivity testing related to both the primary and secondary study endpoints and statistical power calculations. Following this section, there is a description of the methods for testing hypothesis 2, which consists of the ROI analysis.

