## PL1 = b\*PL0 + g\*X + c\*I(V-WHI) + error

where PL0 refers to the baseline WLQ productivity loss and PL1 refers to the post-treatment WLQ productivity loss, X represents a set of covariates such as full-time or part-time stratum assignment, age, gender, baseline depressive symptom severity and, prior depression, and, g represents their regression coefficients, and I(V-WHI) indicates that the veteran is assigned the experimental treatment. The regression coefficient c will be tested by a t-test at 5% significance level of c=0 vs. the alternative c $\Box$ 0. Although we believe that c<0 (the treatment reduces presenteeism) we test against inequality because a two-sided test is conservative and conventional.

The primary analysis is "intent to treat" that is, all persons assigned to each group will be followed up to the maximum possible extent, even if they drop out of IC or V-WHI treatment, and analyzed as a part of their assignment group.

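### Two sites randomize 250 and 100 subjects, but site is named neither as a randomization stratum nor as a covariate; any model that pools them should include it

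*Combined protocol and SAP*

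**What the plan says.** Section R.1 sets the enrolment targets: "CMCVAMC - 250 randomized" and "VA TVHS VAMC - 100 randomized". Section M.2.2 describes allocation: "The randomization procedure will be automated within full/part-time group using a block randomization technique within group". It adds that "Each block of 4 will contain 2 V-WHI and 2 BHL, randomly ordered". The power section repeats the same strata for CMCVAMC's number alone: "we will recruit 250 subjects prior to 50-50 randomization within full time and part time strata".

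The Hypothesis 1 ANCOVA regresses T1 productivity loss on its baseline value, treatment and X, where "X represents a set of covariates such as full-time or part-time stratum assignment, age, gender, baseline depressive symptom severity" and prior depression are given as examples. The baseline randomization check under Sensitivity Testing lists demographic, health and WLQ variables, without site. The secondary and T2 analyses use similar ANCOVAs, and the joint mixed model reuses X. No analysis by site or of site by treatment is described.

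Several features are organised by site. On the comparator, "Usual care will consist of standard behavioral health care at each respective VAMC", and only the CMCVAMC version is then described. Section O.1.1 has TVHS recruiting from its own clinics under its own protocol, with TVHS staff delivering therapy and follow-up there, and states that "all databases will be separate for the two sites".

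**The concern.** Site could plausibly affect T1 productivity loss through case mix, referral route, the care that controls receive and the people who deliver and assess. V-WHI also drops the original program's medical care coordination and relies on the BHL program for it. BHL is introduced as CMCVAMC's integrated care program, so the setting into which the intervention is placed may not be the same at TVHS.

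The consequence depends on how the lists were built, which the plan does not say:

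- **One list over both sites.** Arms balance overall but not within site, and a chance difference in the TVHS share carries over into an unadjusted contrast.
- **Separate lists by site.** Site is in effect a stratum. A model without it leaves between-site variance in the error term, so the standard error is too large.

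Either way, site belongs in a pooled model. Two existing provisions do not supply it. The rule that adds covariates differing between arms at p<0.05 does not name site and has little power to pick it up. The counselor random effect is a sensitivity analysis, and since only V-WHI subjects have a V-WHI counselor, it cannot adjust the controls for site.

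**Working it through.** **The plan's own figures.** The recruitment number reproduces: 200 / (1 − 0.20) = 250. The 83% power (1.2-point difference, 100 per arm, two-sided 5%) cannot be checked independently because no SD is given. Solving for the SD by the normal approximation gives 2.91: the standard error is 2.912 × √(2/100) = 0.412, 1.2/0.412 = 2.91, and Φ(2.91 − 1.96) = 0.83. The noncentral t gives 2.90.

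**Precision lost by omitting site.** Inputs: p = 100/350 from section R.1, so p(1 − p) = 0.204; SD 2.91 as above; adjusted site difference D of 1, 2 or 3 points, an assumption. The added variance is D² × p(1 − p), and the SD without site is √(2.912² + added variance).

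| D | Added variance | Share of residual variance | SD without site | Power, 100 per arm | Power, 140 per arm |
|---|---|---|---|---|---|
| 0, or site in model | 0 | 0 | 2.91 | 83% | 93.2% |
| 1 | 0.204 | 2% | 2.947 | 82.1% | 92.6% |
| 2 | 0.816 | 10% | 3.049 | 79.5% | 90.9% |
| 3 | 1.837 | 22% | 3.212 | 75.2% | 87.8% |

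The last column pools all 350 and applies the 20% total loss, which the plan states for CMCVAMC only, to both sites: 350 × 0.80 / 2 = 140.

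**Chance imbalance if one list serves both sites.** With sites enrolling concurrently in random order, the number of TVHS subjects assigned to V-WHI is approximately hypergeometric, with SD √(100 × 0.5 × 0.5 × 250/349) = 4.2. A simulation of 4,000 block-of-4 allocations, assuming 20% part-time, agrees:

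- SD 4.2 and a 95% range of 42 to 58;
- a 55/45 split or worse in 28% of allocations;
- a 60/40 split or worse in 2.5%.

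Blocking within site by full/part-time reduces the SD to 0.65 and the range to 48–52.

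At a 58/42 split with 175 per arm, the arms differ in TVHS share by (58 − 42)/175 = 0.091. The unadjusted contrast then shifts by 0.091 × D, or 0.18 points at D = 2, against the 1.2-point target. The p<0.05 rule would not catch this even if applied to site: the standard error is √(0.204 × 2/175) = 0.0483, z = 0.0914/0.0483 = 1.89 and p = 0.058.

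**Error rate of the test.** Simulation used 280 analysed subjects, 2,500 runs and a nominal 5%; the Monte Carlo standard error is √(0.05 × 0.95/2500) = 0.4 percentage points.

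| Lists | D | Type I error, site omitted | Type I error, site included |
|---|---|---|---|
| By site | 1 | 5.1% | 5.3% |
| By site | 2 | 3.4% | 4.4% |
| By site | 3 | 3.1% | 4.8% |
| Pooled | 1 | 4.9% | 4.7% |
| Pooled | 2 | 5.4% | 5.2% |
| Pooled | 3 | 5.6% | 5.2% |

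With site-specific lists, omitting site makes the test conservative once D reaches 2. With a pooled list the error rate stays near nominal, so the cost there is precision.

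**The case against.** The strongest reply is one of scope. The form's opening instruction limits its content to what is done with CMCVAMC-recruited Veterans, section M.2.2 gives attrition for CMCVAMC only, and the power section speaks only of the 250. On that reading full/part-time is the natural stratum within a single site. TVHS has its own protocol, not available here, which may describe its own list; this document cites it for recruitment only. If the Hypothesis 1 ANCOVA uses the 250 alone, site is constant and the point falls away. This stands as a reason to ask which population is analysed. It does not settle the matter, because section M.2.2 presents the 250 and the 100 as one randomized trial.

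Other replies also carry weight:

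- The ANCOVA covariates are given as examples. A reader might infer that the plan rules site out, but it does not.
- A reader might infer that usual care is known to differ between sites. The text makes it site-specific but does not describe TVHS care, so any difference and its size are unknown.
- Staff may not be fully separate: section O.1.3 lists CMCVAMC-based counselors and research staff on both sites' staff forms.
- The SD is back-solved and may already contain between-setting variance. A 3-point site difference is about one residual SD, and nothing in the documents supports it. With 350 pooled, power without site stays above the planned 83% in every scenario shown.
- The document postdates August 2016, and Table 2 ends recruitment on 30 September 2016. Allocation may be largely complete, and the authors can only report how it was done.

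**Conclusion.** The omission is real, its consequence is moderate, and it is worth correcting because the remedy is nearly free. The size is small at D = 1 and becomes noticeable only if the sites differ by 2 points or more after adjustment. These figures rest on the back-solved SD, the assumed D, the assumed 20% part-time share and concurrent enrolment; none is a document figure.

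A reader might go further and conclude that the primary comparison is biased or its test invalid. The documents do not support that. Allocation is randomized 1:1, so the estimate is unbiased on average under either list arrangement, and the test is conservative or close to nominal. Nor do they show that the trial is underpowered for want of a site term.

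**What to change.** - Add site as a fixed effect to the Hypothesis 1 ANCOVA, and to the secondary, T2 and mixed models, whenever sites are pooled. The degrees of freedom are the number of contributing sites minus one. Section I mentions three sites in unclear text and a site closed in August 2016; count the closed site if it randomized anyone.
- Report the treatment effect by site descriptively.
- State whether the primary analysis pools the 350 or uses the 250.
- Report whether the randomization lists were in fact site-specific, without asserting site blocking that was not used. For any subjects still to be randomized, block within site by full/part-time group.

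The cost is one or two degrees of freedom and a sentence of text, with no new data to collect.

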# 9.5.6. Include the breakdown of each individual's responsibilities:

- 9.5.6.1. Principal Investigator, responsible for the overall conduct of the study, primarily in providing scientific direction for the project, coordinating activities between the CMCVAMC and Tufts study team, ensuring adherence to best practices and regulatory requirements, and monitoring the implementation and progress of the project.
- 9.5.6.2. Co-Principal Investigator N/A
- 9.5.6.3. Research Coordinator(s) responsible for day-to-day project coordination including supervision of the research assistant working under the supervision of the Principal Investigator; regulatory work, including IRB submissions and maintaining study files and regulatory files.
- 9.5.6.4. Additional research staff by title,

Research Assistant - consent participants and perform baseline (T0) and follow-up assessments (T1 and T2). This will include data entry and management.

Statistician(s) - data quality assessment and statistical analysis; participate in manuscript and presentation development. The CMCVAMC statistician works directly with the Tuft's team statisticians to address all data integrity questions.

Local Clinical Supervisor - serve as the local supervisor to the clinical staff and be the clinical liason between the BHL providers and V-WHI therapists.

Investigators of Tufts Medical Center - responsible for overseeing the Tufts team, preparing and implementing the counselor training and supervision, consulting on the study website and data collection; data analysis and preparing reports, manuscripts and presentations; serve as liaison to VA medical and psychiatric personnel.

Study therapists/clinicians – provide the V-WHI clinical portions of the study; responsible for collaborating/writing notes in clinical charts

Page 22 of 42

- 9.6. Will informed consent be obtained from potential subjects prior to determining eligibility? ☑YES □NO □N/A
  - 9.6.1. If no, provide justification and a HIPAA Waiver of Individual Authorization for Disclosure of Protected Health Information.
- 9.7. Define when a subject is enrolled into the study, e.g. after the subject signs the informed consent or after randomized to treatment. After the subject signs the informed consent
- 9.8. Describe:

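### Fixed blocks of 4 in an open-label trial let enrolling staff who know the block size and keep a tally foresee up to one third of assignments

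*Combined protocol and SAP*

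**What the plan says.** Section M.2.2 (Design) of the combined protocol and SAP describes assignment as "automated within full/part-time group using a block randomization technique within group, where part-time is defined as less than 30 hours per week". It then fixes the block: "Each block of 4 will contain 2 V-WHI and 2 BHL, randomly ordered". The stated reason is caseload: "The small block sizes assure an even flow of new cases to the counselors". On blinding, the same section says that "neither subjects nor the intervention providers will be blinded to subject assignment".

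Section O.1.1 (Study Procedures) places disclosure at enrollment: "Eligible veterans will be randomized at the baseline visit. The veteran will be informed of his/her group assignment and instructed how to proceed". Section R.9.5.6.4 gives the research assistant the tasks of consenting participants, running the baseline assessment and doing both follow-ups. Section R.9.5.3 has study staff contact veterans and invite them in.

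The documents contain no statement that the block size is withheld from enrolling staff, that block sizes vary, or that those staff are blinded. They also do not say whether the sequence is separate for each site.

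**The concern.** Automation hides the list, but it does not stop anyone from inferring the next entry from past ones. With a known block of four in a stratum that staff can identify beforehand, the end of each block can be worked out. A person who knows the next arm can bring one veteran's visit forward or let another's slip. In this trial, a more motivated veteran could be timed to fall in V-WHI.

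The primary outcome is self-reported and treatment is open, so concealment at entry is one of the few protections against bias still available. Selection on unmeasured prognosis would enter the estimated effect directly, and the planned analysis could not remove it.

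**Working it through.** The plan gives no predictability figure, so there is none to reproduce.

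**Inputs from the documents.** Block of 2 + 2, within full/part-time stratum (M.2.2); 250 randomized at CMCVAMC and 100 at VA TVHS (section R.1); target difference of 1.2 points of WLQ productivity loss (W.4.1).

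**Certain assignments.** There are 6 equally likely orders. An assignment is certain once one arm is used up in the block. Positions 1 and 2 are never certain, position 3 is certain with probability 1/3, and position 4 always is.

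- Share = (0 + 0 + 1/3 + 1)/4 = 1/3, that is 8 of 24.
- Counts: 250/3 ≈ 83 at CMCVAMC, 100/3 ≈ 33 at VA TVHS, 350/3 ≈ 117 overall.
- Allowing for two strata and incomplete last blocks, simulation gives 32 to 33%.

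**Best guess** (always guess the arm that is behind): (1/2 + 2/3 + 2/3 + 1)/4 = 17/24 = 70.8%, against 50% with no prediction.

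**If one sequence served both sites** and staff saw only their own site's share p of it, certainty needs both earlier same-arm assignments in the block to be their own, so the share is p²/3.

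- CMCVAMC: p = 250/350 = 0.714, giving 0.51/3 = 17%.
- VA TVHS: p = 100/350 = 0.286, giving 0.082/3 = 3%.

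These are generous, because they also assume that staff know where each block starts.

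**Illustrative bias.** Assume that staff choose veterans whose prognosis differs by d points between the two predicted arms, after covariate adjustment. The documents give no value for d; 0.5 to 1.0 is an assumption.

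- Acting on every guess: bias = d × (2 × 0.708 − 1) = 0.417d, or 0.21 to 0.42 points (17 to 35% of 1.2).
- Acting only on certain assignments: bias = d/3, or 0.17 to 0.33 points.

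**With blocks of 4, 6 and 8 in random order.**

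- Certain assignments: in a simulation with 125 per sequence, and staff who know the set of sizes and the whole history, 2.6%. A larger fixed block helps far less: 25% for 6 and 20% for 8.
- Best guess: the expected number right per block is 2.833, 4.1 and 5.329, so (2.833 + 4.1 + 5.329)/(4 + 6 + 8) = 68.1%.
- Bias if every guess is used: d × (2 × 0.681 − 1) = 0.362d, or 0.18 to 0.36 points, a reduction of 1 − 0.362/0.417 = 13%.
- Bias if only certain assignments are used: 0.026d, or 0.013 to 0.026 points.

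**The case against.** Certainty needs three things together: knowledge of the block size, sight of every earlier assignment in the stratum, and a tally. The documents establish none of these for a named role. Only subjects and intervention providers are called unblinded, section O.1.1 does not say who tells the veteran, and three roles may obtain consent (R.9.5.1.1). This stands as a limit on the claim. It does not remove it: the coordinator handles IRB submissions and so has reason to know the protocol, and the research assistant runs the visit at which assignment is disclosed.

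Room to act is also limited. All criteria must be met before randomization (R.2.2). Diagnosis is confirmed by a diagnostician or a treating provider, work limitation has a numeric threshold of 5%, and candidates arrive by referral. The ANCOVA adjusts for baseline productivity loss, depressive severity, prior depression, age and gender, and Sensitivity Testing adds variables that differ at p<0.05. This largely answers steering on measured severity. Visit timing and unmeasured factors such as motivation remain, since attendance within two weeks is only encouraged.

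Two further points stand. Against someone who acts on every guess, varied blocks reduce the bias by only about 13%; the gain lies in removing certainty. And Table 2 ends recruitment on 9/30/2016 while section I already records a site closure in August 2016, so few randomizations may be left.

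A reader might infer that one third of assignments are in fact known to staff, or that selection took place. The documents support neither. They show a design that permits prediction under stated conditions.

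**Conclusion.** The weakness is real and conditional. Up to 33% of assignments could be foreseen with certainty, and 71% guessed correctly, by staff who know the block size and track all earlier assignments in a site-specific stratum sequence. Separate databases for the two sites (O.1.1) make per-site sequences more likely, but this is not stated; with one shared sequence the certain share is about 17% at CMCVAMC and 3% at VA TVHS at most.

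The bias range of about 0.2 to 0.4 points is a worst case on an assumed steering difference and should not be read as an estimate. Nor should a reader infer that varied blocks make assignment unpredictable: certain assignments become rare, while guess accuracy hardly changes. The change is worth making because it is cheap and protects something the analysis cannot restore.

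**What to change.** For any remaining randomizations, at each site:

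1. In M.2.2, replace the fixed block by computer-generated block sizes that vary at random (for example 4, 6 and 8) within each full/part-time stratum, and state that sequences are separate by site.
2. Keep the block sizes out of every document that enrolling staff see.
3. Require eligibility and T0 to be completed and locked in the data system before the assignment is released. Section R.2.2 already puts eligibility before randomization, but it places T0 only before the start of intervention. T0 supplies the baseline productivity loss used in the primary model.

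The cost is a new randomization list and a few amended sentences. The downside is slightly less even counselor flow: the largest possible imbalance within a block rises from 2 to 4. If recruitment has closed, what remains is to report whether sequences were site-specific and who could see the block size and past assignments.
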